14.0 BIOSTATISTICS

This study was originally designed as a phase II randomized study where patients were randomized 2:1 to respectively receive romiplostim and observational control. The primary endpoint was the achievement of a platelet count of ≥ 100,000/mcL within three weeks of study enrollment, and any patient removed from study during evaluation window without count recovery was considered a treatment failure. Based on earlier MSKCC data, it was estimated that the probability of a success in the romiplostim arm is at least 90%, while the probability of a spontaneous recovery in the control arm is 60% or less.

Due to preliminary trial results, the protocol was amended on 4/13/2016 and the observation control arm was dropped. At that point, the study became a single arm phase II study of romiplostim. The sections below represent the new single arm study design.

Analysis of these data will only be done with 60 evaluable patients enrolled on the trial. There was one patient enrolled during this time who was inevaluable and therefore there were 61 patients enrolled for 60 spots.

Primary endpoint:

This study is a single arm phase II design to evaluate romiplostim mediated improvements in platelet counts in patients who have experienced CIT. The primary endpoint is the achievement of a platelet count of ≥ 100,000/mcL within three weeks of study enrollment. Any patient who is removed from study before the evaluation of the primary endpoint will be considered a treatment failure. A total of sixty patients will be enrolled and treated with romiplostim. Based on preliminary MSKCC data, it is estimated that the probability of a success in patients on romiplostim treatment is at least 90%. Therefore, we will consider the trial promising and worthy of further intervention if at least 54 out of 60 achieve platelet count recovery. The operating characteristics of this design rule are provided in the table below.

	True Rate of Count Recovery						
Probability of	0.85	0.875	0.9	0.925	0.95		
Observing >= 54/60	17%	40%	60%	81%	97%		

Secondary endpoints:

Patients who achieve a platelet recovery may be allowed to resume chemotherapy. In these patients, we are observing for recurrence of chemotherapy-induced thrombocytopenia leading to chemotherapy dose delay or reduction; change in chemotherapy for progression of disease or other cancer related conditions; change in chemotherapy for other toxicities unrelated to thrombocytopenia; and death due to all causes.

Lastly, the frequency of thrombosis, marrow toxicity, and organ dysfunction will be tabulated.

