1.0 PROTOCOL SUMMARY AND/OR SCHEMA

TARGET PATIENTS

- Locally advanced or metastatic solid tumors, and
- Chemotherapy Induced Thrombocytopenia,
 - Thrombocytopenia has persisted for at least 4 weeks despite:
 - > Delay in chemotherapy, and/or
 - Modification of chemotherapy dose/regimen.
- Meets Inclusion/Exclusion criteria
- No mutations associated with myelodysplasia or leukemia by peripheral blood bone marrow cytogenetics and FISH panel.

Romiplostim (Weekly, SQ Treatment) Initial dose: 2 mcg/kg, then titrate per protocol section 9.0, "Treatment/ Intervention Plan"

- Weekly monitoring on Romiplostim per section 9.0, "Treatment/ Intervention Plan:
- First 3 weeks on treatment: Weekly CBC, COMP, LDH, PT, aPTT
- Maintenance on Treatment: Weekly CBC and monthly Comprehensive Chemistry Panel, LDH, PT, aPTT

Primary Endpoint: At 3 Weeks	Proportion of patients achieving ≥100,000/mcL platelets by the end of 3 weeks of treatment.				
Within 3 weeks	Romiplostim (Treatment)				
<100,000/mcL	Failure: terminate from study or continue at the discretion of the investigator.				
≥100,000/mcL	Success: Continue romiplostim at the discretion of the investigator and oncologist.				

At Successful Achievement of Primary Endpoint: Achieve a platelet count of ≥100,000/mcL within 3 weeks.

- Resume chemotherapy regimen at the discretion of the oncologist.
- > Continue weekly romiplostim

Secondary Endpoints:

- 1. Ability to resume and continue two cycles (or 8 weeks, whichever comes first) of chemotherapy without recurrence of Chemotherapy-Induced Thrombocytopenia. We will also observe the following events:12 months of chemotherapy without recurrence of Chemotherapy-Induced Thrombocytopenia.
- 2. Change in chemotherapy regimen for toxicity unrelated to thrombocytopenia.
- 3. Change in chemotherapy regiment for progression of disease or other cancerrelated conditions.
- 4. Death from any cause.

NOTES:

- All Romiplostim treatment will be given as weekly, subcutaneous injections, and doses titrated per protocol section 9.0, "Treatment/ Intervention Plan".
- After the initial 3 weeks of romiplostim on romiplostim, patients who remain on weekly romiplostim will continue to have routine monitoring of weekly CBC and monthly COMP, LDH, and PT/aPTT at discretion of study investigator or oncologist.

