2.0 OBJECTIVES AND SCIENTIFIC AIMS

The primary objective for this study is:

 To evaluate whether romiplostim can improve the recovery of persistent, isolated Chemotherapy-Induced Thrombocytopenia (CIT), to a platelet count ≥100,000/mcL within 3 weeks after initiation of therapy.

Secondary Objectives

The secondary objectives for this study are:

- 1. In patients whose platelet counts have recovered within three weeks on romiplostim treatment, we will observe for:
 - a. Ability to resume at least two cycles (or eight weeks, whichever comes first) of chemotherapy without recurrence of chemotherapy-induced thrombocytopenia leading to chemotherapy dose delay or reduction.
 - i. Note the duration of off-chemotherapy time.
 - b. Change in chemotherapy for progression of disease or other cancer related conditions.
 - c. Change in chemotherapy for other toxicities unrelated to thrombocytopenia.
 - d. Censor patients who have tolerated chemotherapy with romiplostim support for up to 12 months.
 - e. Death due to all causes.
- 2. The safety profile of romiplostim will be assessed in this patient population at specified time-points during the course of study as per section 11.0 Toxicities/Side Effects.

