4.0 OVERVIEW OF STUDY DESIGN/INTERVENTION

4.1 Design

Primary objective:

This is an intent-to-treat multicenter phase II open label trial. Once appropriate patients are identified and enrolled, 60 patients will be enrolled.

During the initial 3-week period, the enrolled patients will receive romiplostim, titrated as per protocol (Section 9.0). Assessment for the primary endpoint will take place at week 3 and denote the proportion of patients that achieves a platelet count of >100,000/mcL within 3 weeks of initiation.

Safety Analysis will be performed at specified time-points (Section 11.0 Toxicities/Side Effects) including possible adverse events such as thrombosis, peripheral blood abnormalities and evidence of organ dysfunction.

Secondary objective:

In patients whose platelet counts have recovered within three weeks, we will observe for patient's ability to receive two cycles (or eight weeks, whichever comes first) of cytotoxic chemotherapy without recurrence of chemotherapy-induced thrombocytopenia leading to chemotherapy dose delay or reduction; change in chemotherapy for progression of disease or other cancer related conditions; change in chemotherapy for other toxicities unrelated to thrombocytopenia; and death due to all causes. The duration for patients off-chemotherapy will also be noted. In addition we are also censoring patients who have tolerated chemotherapy with romiplostim support for up to 12 months.

Safety endpoints will include possible adverse events such as thrombosis, evidence of marrow toxicity, and evidence of organ dysfunction.

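### The trial is labelled intent-to-treat, but the analysis omits one of 61 enrolled patients as inevaluable, with no definition or reason

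*Combined protocol and SAP*

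**What the plan says.** Section 4.1 sets the analysis principle: "This is an intent-to-treat multicenter phase II open label trial".

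Section 14.0 sets the analysis set: "Analysis of these data will only be done with 60 evaluable patients enrolled on the trial". It adds that one enrolled patient was inevaluable, "therefore there were 61 patients enrolled for 60 spots". Neither evaluable nor inevaluable is defined anywhere in the supplied text. The only other use, for cross-over patients in the interim results of Section 3.4, is also undefined.

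Section 14.0 has a rule for early departures: "Any patient who is removed from study before the evaluation of the primary endpoint will be considered a treatment failure". It plans for sixty patients to be enrolled and given romiplostim, and calls the trial promising if at least 54 of 60 recover. Section 12.0 words the primary endpoint for patients receiving romiplostim.

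The start of the three-week window varies. Section 14.0 has "within three weeks of study enrollment". Section 1.0 has "by the end of 3 weeks of treatment", Section 2.0 "within 3 weeks after initiation of therapy" and Section 4.1 "within 3 weeks of initiation". Sections 9.0, 12.0 and 13.0 also count from treatment or its start.

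**The concern.** An intent-to-treat analysis keeps every patient who entered, whatever happened afterwards. Dropping an enrolled patient for an unstated reason is a different analysis. The reader cannot tell whether this patient was untreated, ineligible, removed early or missing platelet counts, and the reason determines how the patient should be scored.

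The proportion recovering is the primary endpoint of a single-arm trial, and the plan measures it against an expected 90%. If the omitted patient did not recover, the proportion reported under an intent-to-treat label is too high.

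**Working it through.** **Inputs.** Enrolled 61, analysed 60, promising if successes reach 54 (all Section 14.0). Let s be the successes among the 60. Assumption: all 61 count as assigned to romiplostim. The documents do not confirm this, because the trial began with a control arm.

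**The plan's own figures.** The table in Section 14.0 gives the chance of at least 54 of 60. The exact value is the binomial upper tail P(X ≥ 54), n = 60:

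| True rate | 0.85 | 0.875 | 0.90 | 0.925 | 0.95 |
|---|---|---|---|---|---|
| Plan | 17% | 40% | 60% | 81% | 97% |
| Exact | 18.5% | 36.4% | 60.6% | 83.9% | 97.0% |

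Three cells agree within 2 points. Those at 0.875 and 0.925 differ by 3.6 and 2.9 points. That is a separate matter and has no bearing on this one.

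**If the omitted patient is a non-success.** The overstatement is s/60 − s/61 = s/3660. The intervals are exact (Clopper-Pearson) 95% and are shown for scale only, since Section 14.0 specifies no interval.

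| s | On 60 | On 61 | Difference |
|---|---|---|---|
| 54 | 90.0% (79.5–96.2) | 88.5% (77.8–95.3) | 1.48 points |
| 57 | 95.0% (86.1–99.0) | 93.4% (84.1–98.2) | 1.56 points |
| 60 | 100% (94.0–100) | 98.4% (91.2–100.0) | 1.64 points |

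Because s/3660 rises with s, 60/3660 = 1.64 points is the maximum.

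**If the omitted patient is a success.** The all-enrolled rate is (s + 1)/61. At s = 54 this is 55/61 = 90.16%, against 90.00%, or 0.16 points higher.

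**Decision rule.** Adding a certain non-success leaves the number of successes unchanged, so the chance of reaching 54 is the exact row above with either denominator. If the patient is a success, the count of 54 is affected only when s is exactly 53, since 53 + 1 = 54.

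**Which reading of the text fits?**

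- *Untreated.* The wording in Sections 12.0 and 14.0 about patients receiving romiplostim would explain a set of 60. No passage says this patient was untreated, and the set would be a treated set, not intent-to-treat.
- *Removed before evaluation.* Section 14.0 would then require the patient to be scored a failure, so the exclusion would breach its own rule.
- *Ineligible or missing counts.* No rule in the supplied text covers exclusion on either ground.

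None of these readings makes the analysis of 60 intent-to-treat.

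**The case against.** The strongest reply is that little depends on this. The shift is at most 1.64 points, against an exact interval about 17 points wide at 54 successes. The only decision criterion is a count, and it does not move if the patient is a non-success. Section 14.0 discloses both 61 and 60, so once the number of successes is reported, a reader can compute the lower rate. There is no randomised comparison to protect, and the references to treated patients make a treated set a natural choice. All of this stands and limits the size of the point. It does not supply a definition or a reason, and it does not make the Section 4.1 label correct.

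Three stronger readings go beyond the documents:

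- *The failure rule has been broken.* That follows only if this patient was removed before evaluation. The text says inevaluable, not removed, and Section 13.0 words its removal list for patients on treatment.
- *The window start decides whether this patient has an outcome.* It matters here only if the patient was never treated or started late, and neither is stated. The differing starts are a separate inconsistency.
- *The exclusion could turn a failed trial into a promising one.* At 54 successes the rate on 61 falls below 90%, but the plan's criterion is the count of 54. It sets no 90% bar on 61 patients.

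**Conclusion.** The point holds as a mismatch between a declared principle and a stated analysis set, made worse by an undefined term and an unexplained exclusion. It should be fixed, but it does not threaten the trial's conclusion.

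If the omitted patient is a non-success, the reported rate is about 1.5 points too high at the threshold and at most 1.64 points too high anywhere, with the 54-success rule unaffected. If the patient is a success, the rate reported at 54 is 0.16 points too low. These figures rest on all 61 having been assigned to romiplostim. If some were not, the all-enrolled denominator is no longer 61.

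**What to change.** In Section 14.0, replace the evaluable-only sentence with a definition along these lines: the primary analysis is intent-to-treat and includes every enrolled patient assigned to romiplostim; a patient with no documented platelet count of at least 100,000/mcL in the window is a failure. State when and why the one patient was inevaluable, and report the 60-patient result as a labelled sensitivity analysis.

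If that patient never received romiplostim, the 60 may instead be defined as a treated (modified) set, without the intent-to-treat label and with the all-enrolled result reported beside it.

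Keep the 54-success rule and name the set to which it applies. Separately, use one window start in Sections 1.0, 2.0, 4.1, 9.0, 12.0, 13.0 and 14.0.

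The cost is a change of wording and a sentence of explanation. The reported rate may fall by up to about 1.6 points. Sample size and decision rule stay as they are, and no new patients are needed.

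### Section 14 sets the 'promising' bar at the planning rate itself, plans no reference rate or confidence interval for the primary proportion, and misstates two of the rule's pass probabilities

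*Combined protocol and SAP*

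**What the plan says.** Section 14.0 first describes the superseded randomized design, for which it was assumed that romiplostim succeeds in at least 90% of patients, "while the probability of a spontaneous recovery in the control arm is 60% or less". It then introduces the single-arm design that replaced it.

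For the single-arm design, "A total of sixty patients will be enrolled and treated with romiplostim", and "Analysis of these data will only be done with 60 evaluable patients enrolled on the trial". The planning statement is "it is estimated that the probability of a success in patients on romiplostim treatment is at least 90" per cent. The rule follows directly from it: "we will consider the trial promising and worthy of further intervention if at least 54 out of 60 achieve platelet count recovery". A table of pass probabilities supports the rule ("The operating characteristics of this design rule are provided in the table below"). It gives 17%, 40%, 60%, 81% and 97% for true recovery rates of 0.85, 0.875, 0.90, 0.925 and 0.95.

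Section 14.0 gives the single-arm design no null or unacceptable rate, no significance level, no test and no interval estimate. The primary objective in Section 2.0 is whether romiplostim can improve recovery to at least 100,000/mcL within 3 weeks. Section 3.4 reports recovery in 13 of 14 romiplostim patients and 1 of 7 observation patients during the randomized stage (Fisher P = 0.0009), and in 18 of 19 of all patients given romiplostim.

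**The concern.** In a single-arm phase II design the cut-off is usually placed between a rate that would be uninteresting and the rate hoped for, so that the hoped-for rate passes with high probability. Here the cut-off is the hoped-for rate. The reasoning runs from the expected rate to the bar and never passes through a rate that the drug has to beat.

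The practical consequence lies just below the bar. With 53 recoveries in 60 patients, the plan gives one output: the criterion was not met. It plans no interval. It also names no benchmark for the single-arm result, although the objective is worded as improvement and two candidate benchmarks stand in the same document (the 60% planning rate and the 1/7 observed in controls). A reader of the final report could not learn from the planned analysis how such a result compares with spontaneous recovery.

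The table is the only justification offered for the rule. It starts at 0.85, so it does not show how the rule behaves at lower rates, including 0.60, and some of its entries looked inconsistent with a binomial calculation.

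**Working it through.** **Inputs.** From Section 14.0: n = 60, cut-off r = 54, planning rate at least 0.90, the five stated pass probabilities, and the 0.60 spontaneous rate from the superseded design. From Section 3.4: 13/14, 1/7 and 18/19.

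**1. Bar against planning rate.** 54/60 = 0.90, which is the planning rate.

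**2. The plan's own table.** The pass probability is the exact binomial tail, P(X ≥ 54) = Σ C(60,k) p^k (1−p)^(60−k), summed over k = 54 to 60.

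| True rate p | Stated | Exact | Difference (stated − exact) |
|---|---|---|---|
| 0.85 | 17% | 18.5% | −1.5 points |
| 0.875 | 40% | 36.4% | +3.6 points |
| 0.90 | 60% | 60.6% | −0.6 points |
| 0.925 | 81% | 83.9% | −2.9 points |
| 0.95 | 97% | 97.0% | 0 |

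The 0.90 and 0.95 entries reproduce, and 0.85 is close. The 0.875 and 0.925 entries do not reproduce. Alternatives were tried at 0.875: cut-off 53 gives 52.0%; cut-off 55 gives 22.3%; n = 61 with cut-off 54 or 55 gives 50.0% or 34.7%; the normal approximation gives 27.9%, or 34.8% with continuity correction. None gives 40%. At 0.925 the same alternatives give 92.2%, 70.6%, 91.5%, 82.9%, 76.9% and 83.7%. None gives 81%.

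**3. Miss probability, 1 − P(X ≥ 54).**

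- p = 0.90: 1 − 0.6065 = 39.4%
- p = 0.925: 1 − 0.8387 = 16.1%
- p = 13/14: 13.5%
- p = 18/19: 3.8%
- p = 0.95: 1 − 0.9703 = 3.0%

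**4. The rule below the range of the table.** P(X ≥ 54) is 2.6 × 10⁻⁷ at 0.60, 0.0002 at 0.70 and 0.031 at 0.80. A pass by chance at a true rate of 60% is therefore not a realistic risk.

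**5. What an interval would show.** The exact (Clopper-Pearson) 95% limits are the 2.5% quantile of Beta(x, n−x+1) and the 97.5% quantile of Beta(x+1, n−x).

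- 50/60: 71.5% to 91.7%
- 53/60: 77.4% to 95.2% (not promising under the rule)
- 54/60: 79.5% to 96.2% (promising under the rule)
- 1/7 in the observation patients: 0.4% to 57.9%

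The results 53/60 and 54/60 fall on opposite sides of the rule, yet their intervals nearly coincide and both lie well above 60%. The lower limit first exceeds 60% at 44/60 (60.3% to 83.9%). At a true rate of 0.90, P(44 ≤ X ≤ 53) = 39.3%, so almost every miss at that rate would still have a lower limit above 60%.

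**6. The reported interim comparison.** Fisher's exact test of 13/14 against 1/7 gives a two-sided P = 0.00085, which agrees with the stated 0.0009.

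**The case against.** The strongest defence is that a strict go/no-go bar is a legitimate phase II choice. Randomization had been dropped after a strongly positive comparison, and a sponsor may then reasonably ask for 90% observed recovery before calling the drug worth pursuing. The protocol does not hide the cost: its own table shows a 60% chance of passing at 0.90. The planning statement is at least 90%, so 39% belongs to the lower edge of the assumed range; near the rates reported in Section 3.4 the miss probability is between about 13% and 4%. This all stands, and it is why the bar itself can stay.

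Three stronger readings are tempting, and the documents do not support them.

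- A reader might infer that improvement over no treatment is never tested. Section 3.4 reports a Fisher test on this trial's own randomized patients. It covers 21 patients and no interim plan for it is described, but it does test improvement. What is absent is any comparison with a stated reference rate in the current single-arm plan.
- A reader might infer that 60% is the only benchmark available. Section 3.4 also gives 1/7 (14.3%) in the observation patients, and even the upper exact limit of that rate, 57.9%, is below 60%.
- A reader might infer that the rule could pass a drug no better than spontaneous recovery, or that 53/60 would be declared no improvement. The first has probability 2.6 × 10⁻⁷ at 60%. The second is not in the text: the rule only withholds the word promising.

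The two table errors are 3 to 4 points in size and do not touch the 0.90 entry.

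**Conclusion.** The point holds as a gap in analysis and reporting, together with an arithmetic error. The single-arm plan uses its planning rate as its pass mark and gives neither a reference rate nor an interval for the primary proportion. A result just under 54/60 would therefore carry a label without a planned estimate. The chance of missing the bar is 39% at a true rate of 0.90, 16% at 0.925 and 3% at 0.95. The table entries at 0.875 (40%, exact 36%) and 0.925 (81%, exact 84%) are wrong; those at 0.85 and 0.90 are off by about one point after rounding.

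These figures assume 60 independent patients with a common recovery probability and the cut-off of 54 as written. Reading the result against 60% further assumes that this planning figure, taken from the superseded design, is still a relevant benchmark. The plan does not say so, and the 1/7 observed in controls suggests that it may be generous.

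**What to change.** In Section 14.0:

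1. Keep 54/60 as the flag for a promising result.
2. Replace the table row with exact values: 0.85, 18%; 0.875, 36%; 0.90, 61%; 0.925, 84%; 0.95, 97%. Add 0.60 (below 0.1%), 0.70 (below 0.1%) and 0.80 (3%).
3. State that the recovery proportion is reported with its exact Clopper-Pearson 95% CI and is read descriptively against the 60% planning rate and the 1/7 recovery among this trial's own observation patients.

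Do not add a formal conclusion of improvement at 44/60, although the lower limit exceeds 60% from that count. Section 14.0 already reports 61 patients enrolled for 60 places, the trial is open label, and Section 3.4 already reports 18/19 responses. A much easier criterion introduced now would be chosen with knowledge of the data, and at a true rate of 0.90 it would be met with probability above 99.9%. If the interval is compared with 60%, label that comparison post hoc unless it is fixed and dated before the primary analysis.

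The cost is a sentence or two and one table row, with no new patients or data. The only downside is that a result below 54 must be described with its interval as well as the flag. The change leaves the 39% miss probability at 0.90 as it is; it makes a miss interpretable.

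### Two of the five probabilities in the 54/60 operating-characteristics table are off by about 3 points or more: 40% at a true rate of 0.875 should be 36%, and 81% at 0.925 should be 84%

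*Combined protocol and SAP*

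**What the plan says.** All of this is in section 14.0 (Biostatistics), under the primary endpoint.

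- Design: "This study is a single arm phase II design to evaluate romiplostim mediated improvements in platelet counts". No interim look or stopping rule is described for it.
- Sample size: "A total of sixty patients will be enrolled and treated with romiplostim". Patients removed before evaluation count as failures, so the denominator stays at 60.
- Decision rule: "we will consider the trial promising and worthy of further intervention if at least 54 out of 60 achieve platelet count recovery". The threshold is drawn from the assumed success rate: "it is estimated that the probability of a success in patients on romiplostim treatment is at least 90" percent.
- Performance: "The operating characteristics of this design rule are provided in the table below". The row labelled "Observing >= 54/60" gives 17%, 40%, 60%, 81% and 97% for true rates of 0.85, 0.875, 0.90, 0.925 and 0.95.
- Enrolment: one patient was inevaluable, so "there were 61 patients enrolled for 60 spots".

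The section does not say how the table was calculated. It names neither a simulation nor an approximation.

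**The concern.** With one stage, a fixed n and a binary endpoint, each cell has an exact value, and two of the printed cells miss it by about 3 points or more, in opposite directions.

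The single-arm design states no null rate, type I error, power or confidence interval. A reader who wants to know how often a treatment with a true rate of 0.875 would pass, or one with 0.925 would fail, has only this table. The same figures could be carried into a report of the trial, where anyone could check them.

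**Working it through.** **Inputs**, all from section 14.0: n = 60; pass if X ≥ 54, that is, at most 6 failures; true rates p = 0.85, 0.875, 0.90, 0.925 and 0.95.

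**Formula.** With X ~ Binomial(60, p), the probability of passing is

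P(X ≥ 54) = Σ (j = 0 to 6) C(60, j) (1 − p)^j p^(60 − j), where j is the number of failures.

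**The two cells in question**, as contributions from j = 0 to 6 failures, in percent:

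- p = 0.875: 0.03 + 0.28 + 1.20 + 3.31 + 6.73 + 10.77 + 14.11 = 36.43
- p = 0.925: 0.93 + 4.53 + 10.82 + 16.97 + 19.60 + 17.80 + 13.23 = 83.87 (the rounded terms add to 83.88)

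**The whole row:**

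| True rate | Printed | Exact | Printed minus exact (points) |
|---|---|---|---|
| 0.85 | 17% | 18.48% | −1.5 |
| 0.875 | 40% | 36.43% | +3.6 |
| 0.90 | 60% | 60.65% | −0.6 |
| 0.925 | 81% | 83.87% | −2.9 |
| 0.95 | 97% | 97.03% | 0.0 |

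With a 2-point allowance, two cells fail. At strict whole-percent rounding four differ, since 0.85 should read 18% and 0.90 should read 61%.

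**Could the row describe something else?** Each alternative below is in percent, for the same five rates in order.

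| Alternative | 0.85 | 0.875 | 0.90 | 0.925 | 0.95 |
|---|---|---|---|---|---|
| At least 53 of 60 | 30.5 | 52.0 | 75.2 | 92.1 | 99.0 |
| At least 55 of 60 | 9.7 | 22.3 | 43.7 | 70.6 | 92.1 |
| At least 54 of 61 | 28.7 | 50.0 | 73.7 | 91.5 | 98.9 |
| At least 55 of 61 | 17.2 | 34.7 | 59.0 | 82.9 | 96.8 |
| Normal, no continuity correction | 13.9 | 27.9 | 50.0 | 76.9 | 96.2 |
| Normal, continuity-corrected | 18.3 | 34.8 | 58.5 | 83.7 | 98.1 |
| Poisson on failures (≤ 6) | 20.7 | 37.8 | 60.6 | 83.1 | 96.6 |
| Arcsine, corrected | 16.7 | 34.4 | 58.4 | 81.5 | 95.6 |

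None gives 40% at 0.875. Rounding the two rates to 0.88 and 0.92 gives 40.9% and 79.8%, which is not the printed 40% and 81% either. A search over every n from 20 to 100, with every cut-off from half of n upward, finds no rule within 3 points in all cells. The best is 46 of 51 (largest error 3.3 points) and the next is 54 of 60 itself (3.6). The row therefore appears to describe the stated rule, with inaccurate entries.

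**Could it be a simulation?** Treat the cells as independent Monte Carlo estimates of the exact values. The standard error of a cell is √(q(1 − q)/R), where q is the exact probability and R the number of replicates. The joint statistic is the sum of the squared standardised deviations, on 5 degrees of freedom.

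| Replicates | Deviation at 0.875 (SE) | Deviation at 0.925 (SE) | Joint chi-square | p |
|---|---|---|---|---|
| 200 | +1.1 | −1.1 | 2.6 | 0.75 |
| 500 | +1.7 | −1.75 | 6.6 | 0.25 |
| 1,000 | +2.3 | −2.5 | 13.2 | 0.02 |
| 2,000 | +3.3 | −3.5 | 26.5 | < 0.001 |

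A run of up to several hundred replicates is compatible with the row, 1,000 fits poorly, and 2,000 can be ruled out.

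**Consequence for reading the table.** The probability of missing the threshold at 0.925 is printed as 100 − 81 = 19% and is 100 − 83.9 = 16.1%. The difference in pass probability between 0.925 and 0.875 is printed as 81 − 40 = 41 points and is 83.87 − 36.43 = 47.4 points.

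**The case against.** The arithmetic is not in dispute. The case on the other side is about weight and cause.

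- **Nothing depends on these cells.** The threshold comes from the assumed 90% rate, and the cell at that rate is within a point. The plan does not label 0.875 or 0.925 as a null, unacceptable or target rate. This stands, and it is why the point ranks as a correction and not as a flaw in the design.
- **The row may be a Monte Carlo estimate and not a miscalculation.** This stands as a possibility for up to several hundred replicates. It does not rescue the table: the plan mentions no simulation, and an exact value is available in one line of code.
- **The contrast between 0.875 and 0.925 is the one where the two errors add.** This is fair. Between the outer rates, 0.85 and 0.95, the printed gap is 97 − 17 = 80 points and the exact gap 97.03 − 18.48 = 78.5, so there the table slightly overstates discrimination. The distortion is local and does not run one way across the row.
- **The figures are pass probabilities, not declared error rates.** This is correct as a matter of labels. They are still the only quantified behaviour of the rule that the plan offers.

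**Conclusion.** The table is wrong as written. For the stated rule, the pass probability is overstated by 3.6 points at a true rate of 0.875 and understated by 2.9 points at 0.925. Two further cells are 1.5 and 0.6 points low, and one is right. This rests only on the plan's own inputs (n = 60, pass at 54 or more, one stage) and on independent patients with a common recovery rate. How the printed values arose cannot be settled from the document. The 54/60 threshold, the sample size and the success decision are unaffected.

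**What to change.** Replace the printed row with 18%, 36%, 61%, 84% and 97%, and label it as exact binomial, n=60. If the current values came from a simulation and are to be kept, state that and give the number of replicates, although the exact values are preferable. The cost is one table row and a label: no patients, and no change to the sample size or the threshold.
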